The study objectives of the COGTIPS study involve assessing an easily-accessible, home-based cognitive function training in individuals with mild subjective cognitive complaints in PD. Our *primary objective* is to assess the efficacy of an online CT program (compared to an active control condition) on executive functions. Our *secondary objectives* are to evaluate CT compared with an active control condition (AC) on 1) the efficacy on relieving subjective cognitive complaints; 2) the durability of the effect after six months, one year and two years; 3) the rate of conversion to PD-MCI and PD-D after one year and two years; 4) the effect on

brain network efficiency and connectivity. Furthermore, we aim to identify baseline brain network characteristics that predict treatment outcome.

Based on previous literature on CT in PD and other neurodegenerative diseases, we hypothesize that compared with an active control condition 1) CT alleviates cognitive –mainly executive– dysfunction in PD patients, 2) CT relieves subjective cognitive complaints in daily-life, 3) the CT effect endures for up to two years after finishing the intervention, and reduces the risk of conversion to PD-MCI and PD-D, and 4) CT improves brain network efficiency and connectivity.

Study design and setting

COGTIPS is a monocenter phase-III randomized controlled trial that will enroll one-hundred-and-forty (140) PD patients. To assess the superiority of the online CT compared with an AC, participants are randomly appointed to either of the conditions in a 1:1 fashion (70 versus 70). Eighty participants (i.e. 40 in each condition) will undergo pre- and post-training neuroimaging to assess CT-specific effects on functional and structural connectivity. This study was approved by the VU University Medical Center Medical Ethical Committee and this protocol is reported in accordance with SPIRIT guidelines [49].

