After 24 intervention sessions, patients are invited for the post-intervention assessment. This assessment will be scheduled as close as possible to the last training session. Participants will first evaluate the intervention with a non-blinded study member. Directly afterwards, participants will undergo a post-intervention assessment ('T1'). This assessment comprises a neuropsychological assessment and questionnaires (see Table 2). One team member (TB) will be de-blinded after the last T1 visit. All assessments after baseline will make use of parallel versions of neuropsychological tasks, if possible.

After six months ('T2'), one year ('T3') and two years ('T4'), participants will again undergo an extensive neuropsychological assessment and questionnaires. At T3 and T4, motor symptoms will also be assessed. From T3 onwards will be a naturalistic follow-up.

Blinding

Outcome assessors will be blinded for the full length of their role as assessor, while non-blinded team members will not assess participants at any point in this study. Blinded study members will not have access to the key of the randomization. Trial participants will be blinded for the full length of the study. Participants will be asked not to share any details of their intervention with the outcome assessor at any point in the study. When the participants' condition is revealed to an outcome assessor, he or she will be replaced by another assessor for this participant.

Drop-outs

Participants that drop out of the study after being allocated to an intervention condition will not be replaced. We expect a low drop-out rate on the basis of our pilot study (one drop-out in 21 participants) and the low burden and short duration of both training conditions. In our sample size calculation, we conservatively account for 10% drop-out.

In case a participant withdraws from the study after four weeks of training (or more), we will aim to schedule an exit-measurement to measure the intervention effect.

Medication adjustments

Participants and their neurologist will be requested to retain a stable medication regime during the study period, specifically during the intervention. Patients and their neurologist will be requested to inform the study team if medication changes are clinically necessary.

Table 2 Tabular overview of the study time schedule including assessments and visits.

Time-point	T-2	T-1	T0	T1	T2	T3	T4
Pre-screening							
Informed consent for pre-screening		X					
SAGE	X						

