- Data on physical activity at each visit will be measured by the New Zealand Physical Activity Questionnaire – Short Form, a structured interview on mild, moderate and vigorous physical activity, as physical activity is known to positively influence cognitive function and potentially provide a neuroprotective effect.[69, 70];
- We will rate motor symptom severity by the Unified Parkinson's Disease – Rating Scale part III and assess disease stage by the modified Hoehn & Yahr stage [71];
- Medication usage data are collected and transformed into a 'levodopa equivalent daily dosage' [33]. Dopamine replacement therapy may influence cognitive functions [72, 73];
- Intervention compliance will automatically be monitored by the training module. We will calculate total compliance as the proportion of completed training games out of 24 total sessions: $[N_{\text{completed}} / N_{\text{total}}] \times 100\%$, in which N_{total} is 13 games x 24 sessions in the CT

condition, and 3 games x 24 sessions in the AC condition. We define non-compliance as a completion rate lower than 75%, in accordance with Petrelli and colleagues [74].

ANALYSIS PLAN

Data-analyses will be performed on the Modified-Intention-To-Treat population, which comprises the compliant participants that underwent at least 75% of the intervention and at least one post-training assessment. We will compare the baseline characteristics of this sample to the Intention-to-Treat population (all randomized subjects). Secondary Per Protocol-analyses will be performed comprising the population that underwent the complete study protocol. Analyses will be performed with IBM SPSS version 22 (Armonk, NY, USA) and in R [75]. We will employ a statistical threshold of $\alpha = .05$.

The primary outcome will be analyzed using a multivariate mixed-model analysis using the accuracy on the five separate task-loadings (S1-S5) of the ToL at post-training visit (T1) as dependent measures, the training condition (CT vs. AC) as independent measure and baseline score of the outcome measures as covariates. We will construct a separate adjusted model with age, sex and years of education as additional covariates of no-interest. No imputation of missing values will be performed as this is not needed in linear mixed models.

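### The main analysis set is selected on at least 75% compliance, and no planned outcome analysis includes all randomised participants as allocated

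*Combined protocol and SAP*

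**What the plan says.** The first paragraph of the Analysis Plan places the data analyses on "the Modified-Intention-To-Treat population, which comprises the compliant participants that underwent at least 75% of the intervention", with at least one post-training assessment as a second condition. The compliance rule stands at the end of Exploratory outcomes and covariates. Completion below 75% counts as non-compliance, a cut-off attributed to a cited trial. Completion is counted in games, out of 13 × 24 in the cognitive training (CT) arm and 3 × 24 in the active control (AC) arm.

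Two other populations are named. The set of all randomised participants has one use: "We will compare the baseline characteristics of this sample to the Intention-to-Treat population (all randomized subjects". The other is narrower than the main set: "Secondary Per Protocol-analyses will be performed comprising the population that underwent the complete study protocol". The paragraphs on the primary, secondary, conversion and imaging analyses name no further population.

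Study design and setting gives the aim: "To assess the superiority of the online CT compared with an AC, participants are randomly appointed to either of the conditions". Under Drop-outs, the plan seeks an exit-measurement from participants who withdraw at four weeks or later, and its stated purpose is to estimate what the intervention did.

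**The concern.** Randomisation makes the arms comparable at allocation. Removing people for what they did afterwards can undo that. The criterion here is adherence to two quite different regimens. CT is 13 games that adapt to keep participants at their limit; AC is solitaire, trivia and hangman. The documents do not show that non-compliance will differ by arm, but they give no reason to assume that it will be equal.

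The label matters too. A reader who sees a modified intention-to-treat result will expect something close to the randomised comparison, and this set is defined by adherence. Because the only other outcome set is stricter, no all-randomised estimate would stand beside the main result to show whether selection had mattered. The planned comparison of baseline characteristics covers measured variables only and estimates no treatment effect.

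**Working it through.** **1. Who enters which analysis**

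| Set | Condition after randomisation | Planned use |
|---|---|---|
| Intention-to-Treat | none | baseline characteristics only |
| Modified-Intention-To-Treat | at least 75% of the intervention and at least one post-training assessment | outcome analyses |
| Per Protocol | complete study protocol | secondary outcome analyses |

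Both sets used for outcomes are conditioned on adherence.

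**2. Exit-measurements without a use**

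The threshold is 0.75 × 13 × 24 = 234 of 312 games in CT and 0.75 × 3 × 24 = 54 of 72 in AC. Intervention characteristics sets three sessions a week for eight weeks. For fully completed, on-schedule sessions:
- week 4 is 12/24 = 50% (156 games in CT, 36 in AC);
- 17 sessions is 17/24 = 70.8% (221 and 51 games);
- 18 sessions is 75% (234 and 54 games).

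Exit-measurements after 12 to 17 such sessions would be sought and then fall outside both outcome sets. Skipped games or slower schedules move these session counts; the rule itself is in games.

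**3. Possible bias when there is no true effect**

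The documents give drop-out (1 of 21 in the pilot, 10% planned) but no non-compliance rate. All rates below are therefore assumptions, with 70 per arm and the plan's pre-post correlation of .6.

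*Model A.* Outcome = .6 × baseline + .3 × U + error, with U unmeasured; adherence = .6 × U + .8 × noise; the lowest p in each arm is excluded. The bias is .3 × .6 × (difference between arms in truncated-normal means). Type I error comes from 100,000 simulated trials per scenario.

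*Model B.* Non-compliers score s SD below compliers, with s from 0.25 to 0.75. The bias is (q₁ − q₂) × s, where q₁ and q₂ are the excluded fractions. The standard error is √(1 − .6²) × √(1/n₁ + 1/n₂).

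| Excluded, arm 1 vs arm 2 | Model | Bias (SD) | Type I error |
|---|---|---|---|
| 10% vs 10% | A and B | 0 | 5.0% |
| 12% vs 8% | A | 0.012 | 5.2% |
| 15% vs 5% | A | 0.030 | 5.5% |
| 15% vs 5% | B | 0.025 to 0.075 | 5.4% to 8.2% |
| 20% vs 5% | B | 0.0375 to 0.1125 | 5.8% to 12.1% |

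The last row is 0.0375/0.23 = 16% to 0.1125/0.23 = 49% of the planned g = .23. If those excluded would have scored worse, the arm with more exclusions is favoured; swapping the rates reverses the sign. In the Model A runs, analysing everyone as allocated gave a bias of −0.001 to 0.000 SD and a type I error of 4.9% to 5.2%.

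**4. What an as-allocated analysis costs in precision**

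The plan's own figure comes first. For a repeated-measures ANOVA interaction, λ = f² × N × 2/(1 − r). With f = .12, r = .6 and N = 112, λ = .0144 × 112 × 2/.4 = 8.06 and power is 0.804, so the stated 112 reproduces.

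Now assume that a fraction p are non-compliers who gain nothing and that all 140 are measured with equal residual SD. The effect is multiplied by (1 − p) and the standard error by √(1 − p). The effect-to-SE ratio, relative to the 75% set, is then √(1 − p).
- p = 10%: 0.949. Power is 0.81 (N = 140, f = .108) against 0.85 (N = 126, f = .12).
- p = 20%: 0.894. Power is 0.71 (N = 140, f = .096) against 0.80 (N = 112, f = .12).

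The ratios do not depend on the planned effect; the power figures take f = .12 as given.

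**The case against.** The strongest reply is that the cut-off is prespecified and has a precedent, that adherence is actively supported, and that any bias is probably small. Much of this stands. Prespecification rules out a data-driven cut-off. Eight-week intervention period provides weekly compliance checks, biweekly questionnaires and telephone follow-up. At average exclusion near 10% with mild selection, the illustrated bias is at most about 0.03 SD. None of it restores a comparison of the groups as randomised, or supplies an estimate that would reveal a problem if non-compliance proved larger or uneven.

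A second reply is timing. The amendments run to October 2020, Appendix 1 describes the scans in the past tense, Table 2 places imaging at T0 and T1 only, and one team member is to be de-blinded after the last T1 visit. T1 may therefore be finished, and replacing a prespecified primary set after de-blinding would itself be a post hoc change. This stands, and the fix allows for it.

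Three stronger readings are tempting but not supported:
- A reader might infer that anyone short of 24 sessions is refused T1, because "After 24 intervention sessions, patients are invited for the post-intervention assessment". The same paragraph ties the visit to the last training session. A strict 24-session condition would make the 75% rule largely redundant at T1, and the T2 to T4 visits carry no session condition. The text is unclear; it does not exclude these participants.
- A reader might count the missing-data statement, "No imputation of missing values will be performed as this is not needed in linear mixed models", as part of the same fault, since the primary model uses T1 alone. The condition of one post-training assessment serves the T2 to T4 analyses as well, and missing T1 data is a separate question from selection on compliance.
- A reader might treat the main set and the Per Protocol set as one. They are distinct, and the Per Protocol set is stricter.

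**Conclusion.** The point holds. The main set is selected on post-randomisation adherence, its label suggests otherwise, and no planned outcome analysis keeps all randomised participants as allocated. This follows from the text without any assumption.

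The size is unknown. A reader might infer that the result will be biased, or biased in favour of CT. The documents support neither: bias needs exclusion that differs by arm and is related to outcome, and they give no non-compliance rates and no such relation. The range in the working, from 0 to 0.11 SD, rests wholly on assumed exclusion rates and assumed differences between compliers and non-compliers. The case for change rests on the missing as-allocated analysis, which costs little to add; it does not rest on a demonstrated bias.

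**What to change.** - Analyse all randomised participants as allocated, regardless of compliance, using all T1 data and the exit-measurement where T1 was not done. Make this the primary analysis if the plan can still be changed before unblinding. Otherwise add it as a clearly dated analysis, reported beside the prespecified one.
- Add two sensitivity analyses: one that leaves exit-measurements out, because their timing differs from T1, and one that shifts the assumed mean of missing outcomes separately by arm.
- Keep the 75% analysis as supportive, under a label such as compliant set.
- Report by arm, with reasons, how many participants each set excludes and how many lack T1 data.
- If T1 visits are still under way, state under Post-intervention assessments that participants are invited whatever number of sessions they completed.

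The cost is SAP wording, refitting the planned models on the larger set, one table, and possibly some extra T1 visits within the existing schedule. The number of visits is not known; each 10% of participants stopping short would be 0.10 × 140 = 14. The statistical price is the dilution calculated above: modest at 10% non-compliance and a real loss of power at 20%. The plan should state it openly.

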An active control condition is used to correct for the nonspecific cognitive activity that participants in the CT group go through. In the control condition, participants undergo cognitive engagement using three games (i.e. solitaire, trivia questions and hangman) with a total duration of 45 minutes that will sequentially be performed and are hypothesized not to train specific cognitive functions.

Outcomes

Primary outcome

The primary outcome is the efficacy of CT on executive functions, measured by the percentage correct change score on a previously used computerized self-paced version of the Tower of London (ToL) task [29]. The ToL measures several aspects of executive functions, including planning, inhibition, and working memory [61]. This neuropsychological task consists of a model of three pins with different lengths, and three differently colored beads. In this task, the goal is to get from a starting position to a target position in as minimal steps as possible. There are five planning conditions that range in difficulty, with possible solutions ranging from one to five steps (i.e. task-load S1-S5). After nine exercise items with feedback, 100 pseudo-randomized test trials will be presented with a maximum response duration of 45 seconds per trial and no feedback on accuracy.

Secondary outcomes

The secondary outcome measures include (i) subjective cognitive complaints, (ii) cognitive function (other than the ToL) and (iii) structural and functional connectivity and brain network characteristics. All outcomes described below are changes after intervention relative to baseline.

- 1) Subjective cognitive dysfunction change after the intervention will be measured by the Parkinson's Disease Cognitive Functional Rating Scale (PD-CFRS, [62]) score and the Cognitive Failures Questionnaire (CFQ) score at the end of the intervention (T1), and at follow-up (T2, T3, and T4). We use the PD-CFRS questionnaire as a Parkinson-specific and sensitive measurement of subjective cognitive function. This questionnaire will be filled out by the participant and if possible by a caregiver. We will additionally use the CFQ as this measure has been used more frequently and it is more sensitive to small cognitive errors in daily living such as memory problems, absent-mindedness and slips of action[63];
- 2) Cognitive function change after the intervention will be measured by

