The secondary outcome measures will also be analyzed with linear mixed-models with baseline score of the outcome measures as covariates. Subjective cognitive dysfunction will be modeled with the total score of the PD-CFRS (both self-report and caregiver) and the CFQ a) at post-training (T1) and b) at all follow-up assessments (T2, T3 and T4) as dependent variables. We will perform a factor analysis on all neuropsychological assessment outcomes (see Table 2) at baseline using a factor analysis with regularized maximum likelihood estimation to produce latent cognitive traits. We will compute baseline trait scores (i.e. factor scores), and compute trait scores at follow-up measurements based on the baseline factor analysis. The effect of CT on cognitive functions will be assessed with a multivariate mixed-model comparable to the above, using the trait scores as dependent variables. The effect of CT relative to AC on neuropsychiatric symptoms will be analyzed using similar multivariate mixed-models with as dependent variables the Beck Depression Inventory, the Parkinson Anxiety Scale, the Apathy Scale and the Questionnaire for Impulsive-Compulsive Disorders in Parkinson's Disease – Rating Scale. Covariates will be added to the regression model based on a change-in-estimate method if there is a change of $\geq 10\%$ of the regression coefficient for the intervention variable.

In order to analyze between-group differences in conversion to PD-MCI or PD-D, we will first classify patients at baseline, T3 and T4 as having normal cognition, PD-MCI or PD-D. We define conversion 'down' as conversion to a milder cognitive dysfunction classification, no conversion as classification in the same category at a later assessment visit and conversion

'up' as conversion to a worse cognitive function classification. We will assess the association between the intervention and conversion rate with a Fisher's exact test. Odds ratios and confidence intervals of the conversion 'down' and no conversion groups versus the conversion 'up' group will be computed as a measure of effect size.

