We will perform Fisher's exact tests to verify if the demographic and clinical characteristics of the MRI subsample are similar to those of the full study sample. Functional MRI and diffusion tensor imaging data will be (pre)processed and analyzed with Statistical Parametric Mapping (SPM) software, FMRIB Software Library (FSL) and in-house Matlab (The MathWorks, Inc, Natick, MA, USA), scripts in combination with open-source toolboxes for (dynamic) network analysis [67, 68] to study the effects of cognitive training on the functional and structural brain network, respectively. We will also employ typical independent component analysis in combination with dual regression for resting-state functional connectivity and morphometric (e.g. cortical thickness) analysis on T1-weighted structural MRI to study within and between group-effects of our intervention. Moreover, to establish treatment response at the individual level, Multivariate Pattern classification ('machine learning') analyses will be performed to identify predictive markers (clinical, neuropsychological and neuroimaging) to be able to predict (in future patients) who is most likely to benefit from cognitive training.

Sample size

The sample size calculation is performed on the basis of a previous meta-analysis on the effects of CT on cognitive function [22]. This study showed an effect size of Hedges $g = .23$ (i.e. $f = .12$), based on the effect of CT on improving *global* cognitive function. The sample size needed to detect this effect is 112, based on a repeated-measures analysis of variance, corrected for a moderate correlation between pre- and post-treatment measures (i.e. $r \approx .6$). This sample size estimation also provides a good indicator for the power of our multivariate mixed-model regression analysis with adjustment for baseline measures.

To ensure adequate power for the secondary study parameters, i.e. the development of PD-MCI and PD-D at one and two years follow-up, with an $\alpha = .05$ and $\beta = .8$, and based on a small drop-out ($\sim 10\%$) given the home-based, easily-accessible training, we will include 140 participants.

References

1. Jankovic J: **Parkinson's disease: clinical features and diagnosis.** *Journal of neurology, neurosurgery, and psychiatry* 2008, **79**:368-376.

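### Randomisation is stratified by education, but the main primary model omits the stratum; adding it is a small, nearly free gain, and the deciding test should be named in the same edit

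*Combined protocol and SAP*

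**What the plan says.** **Stratification.** Under Condition allocation and instructions, the randomisation sequence has two strata. Lower education is Verhage level 5 or below, described as comparable to 11 years or less; higher education is level 6 or 7, comparable to 12 years or more. No block size is given.

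**Primary model.** The Analysis Plan specifies a multivariate mixed model "using the accuracy on the five separate task-loadings (S1-S5) of the ToL at post-training visit (T1) as dependent measures", with "the training condition (CT vs. AC) as independent measure and baseline score of the outcome measures as covariates". A second, separate model adds age, sex and years of education. The stratum is not in the main model. One alpha of .05 is set, with no multiplicity rule.

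**Primary outcome.** Under Outcomes, efficacy is "measured by the percentage correct change score on a previously used computerized self-paced version of the Tower of London (ToL) task", which is a single score. The task has five loads and "100 pseudo-randomized test trials will be presented with a maximum response duration of 45 seconds per trial"; the number of trials per load is not given. Study objectives sets one primary aim: to "assess the efficacy of an online CT program (compared to an active control condition) on executive functions".

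**Sample size.** "The sample size needed to detect this effect is 112, based on a repeated-measures analysis of variance". The plan treats this figure as a good guide to the power of the multivariate model.

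**The concern.** When randomisation is stratified on a factor related to the outcome, arms that are balanced within strata give a more precise treatment comparison. A model that leaves the factor out still gets the more precise estimate, but attaches a standard error that is too large, because the between-stratum variation stays in the residual. The test is then slightly conservative and some power is lost. Education plausibly relates to Tower of London accuracy. It is used to allocate participants, yet it is absent from the model that carries the primary conclusion.

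A second, lesser matter sits in the same paragraph of the plan. One score is defined as primary, five load accuracies are modelled, and the coefficient, contrast or joint test that decides the question is not named.

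**Working it through.** **1. The plan's own figure.** Inputs from Sample size: f = .12, pre-post correlation r about .6. Assumed: two-sided alpha .05, and power .80 applying to the 112. For the group-by-time interaction with two arms and two occasions:

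λ = f² × N × 2/(1 − r) = .0144 × 112 × 2/.4 = 8.064.

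F with 1 and 110 df gives power .804, so 112 is reproduced. It is a 1-df calculation.

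**2. Starting points at N = 140 × .9 = 126.** The effect size can be read in three ways, so all three are carried:

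- A: f = .12 as the interaction effect on a change score. λ = .0144 × 126 × 2/.4 = 9.072.
- B: the same f, as a difference of 4f = .48 SD, with baseline adjustment. λ = (126/4) × .48²/(1 − .6²) = 11.34.
- C: g = .23 as the between-arm difference at T1, with baseline adjustment. λ = (126/4) × .23²/(1 − .6²) = 2.604.

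**3. Effect of omitting the stratum.** Let R² be the share of post-baseline variance that the stratum explains. The documents do not give it; 5% and 10% are assumed. With arms balanced within strata, the true variance of the estimate is multiplied by (1 − R²), so the noncentrality is λ/(1 − R²) in both models.

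- With the stratum: noncentral t, 122 df, usual critical value.
- Without it: the standard error uses the full variance, so the effective critical value is t/√(1 − R²). With 123 df, 1.979 becomes 2.031 (R² = 5%) or 2.087 (R² = 10%). Type I error is then .044 or .039.

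| Reading | R² = 5%: power without → with | R² = 10%: power without → with |
|---|---|---|
| A | .854 → .866 | .861 → .883 |
| B | .922 → .929 | .927 → .941 |
| C | .357 → .376 | .353 → .393 |

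The gain runs from .007 (B, 5%) to .040 (C, 10%).

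A simulation check (8,000 trials per cell, 50:50 strata, Monte Carlo standard error about .002) gave type I error without the term of .044 and .036 under balance. Under simple randomisation it was .049 and .052.

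**4. The deciding test.** If effects on the loads are pooled with equal weights, the result equals overall percent correct only when each load has 100/5 = 20 trials. The plan does not say so.

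Pooled and 5-df joint tests both hold alpha at .05 but suit different effect patterns. As an illustration, take N = 126, between-load correlation .5 (assumed), equal variances, and reading A applied to each load:

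- Equal effect on all five loads: pooled power .971, joint .851.
- Effect rising as 0, .25, .5, .75 and 1 times f over S1 to S5: pooled .49, joint .85.

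The ranking depends on the effect pattern, about which the documents say nothing.

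**The case against.** **Against the education point.** The separate model already includes years of education, and the strata are tied to years. Baseline Tower of London scores may absorb most of what education explains, so R² could be below 5%. No block size is stated, so balance within strata is itself an assumption; under simple randomisation type I error is about .05. All of this stands and limits the size. It does not remove the point, because the main model carries the conclusion and lacks the factor used to allocate participants.

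**A stronger reading of the five accuracies.** A reader might infer that five outcomes at .05 mean an inflated type I error. If any one load counted as success, the two-sided familywise error would be 1 − .95⁵ = .226 with independent loads, falling to .209, .183, .148 and .102 for assumed between-load correlations of .3, .5, .7 and .9. Counting only results that favour training, it would be about .12 down to .05, against .025 for a pooled test. The documents do not support that inference. No section says one load suffices. Condition is the only independent measure, no condition-by-load term is listed, there is one primary objective, and N = 112 comes from a 1-df test. The singular wording "regression coefficient for the intervention variable" points the same way, but weakly, since it belongs to a covariate rule in the secondary-outcome paragraph. Choosing the pooled test over a joint test is also partly preference, as the two effect patterns show.

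**A stronger reading of the stratum.** A reader might also infer that omitting it makes the primary test invalid. It does not: the test keeps its level or errs on the cautious side.

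**Conclusion.** The point holds as a minor improvement. Leaving the education stratum out of the main primary model costs roughly .01 to .04 of power at 126 evaluable participants and lowers the actual type I error to about .04. Both figures rest on balance within strata and on an assumed R² of 5% to 10%. The power levels depend on how the effect size is read; the direction of the gain does not.

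The unnamed deciding test is underspecification. On the natural reading, a 1-df condition effect pooled over S1 to S5, alpha stays at .05, and the analysis matches both the single score under Outcomes and the calculation behind 112. It merits a sentence of clarification alongside the model change.

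**What to change.** In the Analysis Plan paragraph on the primary outcome:

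1. Add the two-level education stratum used at randomisation to the main primary model. Keep the model with age, sex and years of education as a sensitivity analysis.
2. Name the single deciding test. The natural choice is the two-sided .05, 1-df condition effect on T1 accuracy pooled over S1 to S5. State whether pooling means equal weight per load or all 100 trials together.
3. Label load-specific effects and the condition-by-load interaction as secondary.

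The cost is about two sentences and 1 df for a covariate already collected, with no new data and no change to the sample size.
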